## **Ib. Objectives/Purpose of the study**

Our objective is to conduct a prospective randomized trial to assess the utility of using real-time ultrasound imaging in the reduction of forearm fractures in the PED. We also plan to assess provider satisfaction with using ultrasound for the reduction procedure compared to fracture reduction without use of ultrasound. We hypothesize that the use of ultrasound will improve patient outcomes and provider satisfaction. Thus, the primary outcome of the study will be:

- 1) To compare the number of patients requiring a repeat reduction procedure between the experimental group (ultrasound guided fracture reduction) and control group (standard of care forearm fracture reduction).

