### **Secondary Outcomes:**

- 1) To compare provider satisfaction with the reduction procedure between the two groups. Specifically, we will ask providers to determine:
  - I. Providers from experimental group:
    - a. Ease of fracture reduction - scale 1-5, (1=easy 5=very difficult)

---

Ang et al, Ultrasound-guided reduction of distal radius fractures, Am J of Emerg Med, 2010; 28, 1002-1008

Chinnock et al, Ultrasound-guided reduction of distal radius fractures, J of Emerg Med, 2011, 40 (3) 308-312

 Brahm J et al, A Randomized controlled trial of emergency department ultrasound-guided reduction of distal radius fractures, Annals of Emerg Med-Abstracts, 2011 Oct; 58(4), 230

IRB #:

Version 1.2

- b. Ease of using ultrasonography on a 5 point scale (1=easy, 5=very difficult).
- c. Was ultrasound helpful in completing the fracture reduction? a) yes b) no c) uncertain

II. Providers from control group:

- a. Ease of fracture reduction - scale 1-5, (1=easy 5=Most difficult)
- b. Do you think real-time imaging would have been helpful for this reduction?

|

- 2) To compare the adequacy of reduction between groups by measuring and comparing the degree of angulation and displacement on the post reduction x-rays. An orthopedic surgeon who is blinded to the patient's group assignment will read the x-rays. The acceptable degree of angulation will be the same in both groups. The acceptable degree of angulation based on age is less than 20 degrees' angulation for patients younger than 10 years of age and less than 10 degrees' angulation for patients older than 10 years of age.
- 3) To compare the time for the fracture reduction procedure between the experimental and control group.
- 4) To compare the number of patients requiring operative repair after reduction between the experimental and control group.
- 5) To compare the post-reduction ultrasound and x-ray interpretation, including measurement of degree of angulation and displacement on the ultrasound and x-ray for each patient.

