#### | **Ic. Study Design**

The study will be a prospective randomized, controlled, single blinded study. The study is single blinded in that the orthopedic surgeon reading the x-rays and determining the degree of angulation and displacement will be blinded to all patient characteristics and the patient's group assignment.

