While it has been our experience that the majority of reduction procedures performed in the PED are done without the use of any real time imaging, some orthopedic surgery residents employ the use of the c-arm (fluoroscopy) and/or a portable x-ray machine during the reduction procedure. At his/her discretion, the orthopedic resident may use either of these modalities in both the ultrasound and control group as per standard of care in the PED. The use of these modalities will be recorded.

After the reduction procedure in the ultrasound group and prior to reviewing the post reduction x-ray, the orthopedic resident will complete a brief questionnaire with the following questions.

For the experimental group:

- a. Rate the ease of fracture reduction from 1-5, (1=easy 5=Very difficult)
- b. Was ultrasound helpful in completing the fracture reduction? a) yes b) no c) uncertain
- c. Rate the ease of using ultrasonography on a 5 point scale (1- easy, 5=very difficult).

The control group will undergo fracture reduction without ultrasound guidance as per the current standard of care in the PED. After the reduction procedure in the control group, the orthopedic resident will complete a brief questionnaire with the following questions:

For the control group:

IRB #:

Version 1.2

- a. Rate the ease of fracture reduction from 1-5, (1=easy 5=very difficult)
- b. Do you think real-time imaging would have been helpful for this reduction?

After the reduction and casting is completed, patients in both groups will undergo a post-reduction x-ray. Based on the degree of displacement on the x-ray, the orthopedic surgeon will determine whether the patient needs a repeat reduction, as per routine standard of care. If a repeat reduction is required, the treating physician can choose to use ultrasound at his/her discretion. The angle of displacement will be measured on the post-reduction x-ray by an orthopedic surgeon. Additionally, the angle of displacement measured on the post-reduction ultrasound will be measured and compared to the angle of displacement on the post-reduction x-ray. An expert sonographer will review cases where the ultrasound and x-ray results do not correlate.

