### **IIIb. Data Collection / Monitoring**

The primary endpoint of the study is comparing the percentage of patients with an adequate degree of angulation on post-reduction x-rays between the experimental group and the control group. X-rays will be performed based on the PED routine standard of care.

Demographic data recorded by the study trained physician will include the patient's name, age, medical record number, date of birth, date of visit, and ultrasound experience of the study-trained physician performing the ultrasound. *The patient identifiers are necessary for patient tracking to match ultrasound findings with X-ray final readings and for clinical follow up.* Type of sedation used, length of procedure and any ultrasound data will be collected and recorded by study trained physicians. Radiographic readings will be collected by the investigators.

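### The repeat-reduction outcome rests on a decision with no named decider, stated blind or numeric criterion; the single blind covers only the x-ray measurement

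*Combined protocol and SAP*

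**What the plan says.** **Primary outcome.** Section Ib gives it as "To compare the number of patients requiring a repeat reduction procedure between the experimental group (ultrasound guided fracture reduction) and control group". The Number of Subjects section sizes the trial on 25% against 6%. The 6% is a repeat-reduction rate; the 25% (5 of 20 charts) also counts operative management.

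**Who decides.** Section IIIa has every patient x-rayed after casting. It then says that "the orthopedic surgeon will determine whether the patient needs a repeat reduction, as per routine standard of care", and the film is the stated basis for this decision. The surgeon is not identified further, and no cut-off, blind or adjudication is attached to the decision.

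**Who is blinded.** Section Ic: "The study is single blinded in that the orthopedic surgeon reading the x-rays and determining the degree of angulation and displacement will be blinded", both to patient characteristics and to group.

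**Common limit.** Secondary outcome 2 sets age-based angulation limits and says "The acceptable degree of angulation will be the same in both groups". The limits belong to the adequacy comparison and are not tied to the decision to repeat.

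**Competing definition.** Section IIIb describes the primary endpoint as "comparing the percentage of patients with an adequate degree of angulation on post-reduction x-rays".

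**The concern.** A reader who sees the trial described as single blinded would expect the blind to protect the primary outcome. For the outcome in Ib it does not appear to. The blinded reading feeds a secondary comparison, while the primary count depends on a clinical decision made under routine care, probably by someone who knows whether ultrasound was used.

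A film that is clearly good or clearly bad leaves little room for influence, but a borderline film leaves some. In the ultrasound arm the operator has already judged the alignment satisfactory on ultrasound before seeing the film, and Ib states the expectation that ultrasound will do better. If such knowledge moved decisions, the repeat rates could differ with no difference in bone position, and the trial would report that as a treatment effect. With about 17 events planned in total (56 × 0.25 = 14 and 56 × 0.06 = 3.4), a few decisions carry weight.

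**Working it through.** **1. What the text fixes about the decider.**
- IIIa says the consulting orthopedic surgeon chooses closed reduction and performs it. Later it calls the operator the orthopedic resident and the person deciding on a repeat the orthopedic surgeon.
- These may be one person or two. Either way the decider probably belongs to, or works with, the team that did the procedure, and that team knows the arm.
- IIIa lists measurement of the post-reduction angle as a separate step, by an orthopedic surgeon. Ic keeps the reader unaware of all patient characteristics. That is hard to square with a routine clinical decision, so reader and decider are unlikely to be the same person. The protocol does not settle it.

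**2. The plan's own figure.** Inputs from the Number of Subjects section: p1 = 0.25, p2 = 0.06, power 80%, alpha 0.05 (taken as two-sided; sidedness is not stated). With p̄ = 0.155:

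n = [1.960·√(2·0.155·0.845) + 0.842·√(0.25·0.75 + 0.06·0.94)]² / (0.19)² = (1.003 + 0.416)² / 0.0361 ≈ 55.8, so 56 per group.

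The stated size is reproduced and is not in question here.

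**3. What shifted decisions could do.** The documents give no figure for this, so the shares below are assumptions. Suppose there is no true effect, 25% of patients in each arm would be re-reduced under arm-blind decisions, and a share w of those repeats is withheld in the ultrasound arm only. The observed ultrasound rate is then 0.25·(1 − w). The test is the planned chi-square (taken without continuity correction): with a and b events, t = a + b and n = 56, X² = 2n(a − b)² / [t(2n − t)], significant at 3.84 or more. Summing the binomial probabilities of all significant tables gives:

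| w | Ultrasound rate | Mean decisions changed (14·w) | Chance of significance | Of which favoring ultrasound |
|---|---|---|---|---|
| 0 | 25.0% | 0 | 5.1% | 2.5% |
| 10% | 22.5% | 1.4 | 6.2% | 5.0% |
| 20% | 20.0% | 2.8 | 9.8% | 9.3% |
| 30% | 17.5% | 4.2 | 16.5% | 16.3% |
| 40% | 15.0% | 5.6 | 26.7% | 26.7% |

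The arms are equal in size, so withholding the same shares in the control arm gives the same chances of significance, mostly in favor of control.

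If the true effect were half the planned one (25% against 15.5%), the chance of significance would rise from 24.4% with no shift to 32.1%, 41.1% and 51.0% with 10%, 20% and 30% withheld.

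**4. Whether the planned blinded reading already serves as a check.**
- Secondary outcome 2 compares the blinded reading between arms but does not link it to the decision to repeat.
- It does not say which film is read when a patient has more than one. After a repeat, IIIa lets the physician use ultrasound in either arm, so a later film no longer reflects the assigned procedure.
- The numeric limit covers angulation only, while the repeat decision rests on displacement, a word IIIa uses for both an angle and a distance.
- The limits cover patients under 10 and over 10 years; age exactly 10 is not assigned.

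**The case against.** Several counter-arguments have force.

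- **The decision is anchored to the x-ray.** This stands and limits any bias. It does not remove it, because no criterion governs the borderline film.
- **IIIb's endpoint is protected.** This stands. If adequate angulation governs, the blinded reading largely covers it and the exposure falls on another outcome. But Ib and the sample size point to repeat reduction, so the conflict has to be resolved rather than relied on.
- **The arms are less different than they look.** IIIa permits c-arm or portable x-ray in both groups and records their use, so some control operators will also have had imaging. This weakens any assumed contrast in the operators' confidence.
- **A blinded comparison by arm already exists.** Secondary outcome 2 provides one, with a common limit. Only the link to the repeat decision, the choice of film and a statement of what is not blinded are missing.

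A reader might go further and infer that the decider is the unblinded operator acting at will, and that the result must lean toward ultrasound. The documents do not support that. The decider is unnamed and knowledge of the arm is an inference. The discretion IIIa grants concerns imaging tools, not whether to repeat. Nothing in the documents fixes the direction or size of a shift.

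**Conclusion.** The gap is real and moderate. For the primary outcome in Ib, the protocol names no decider, states no blind and sets no criterion, and its single blind protects a different measurement. Knowledge of the arm is likely, and it could move borderline decisions.

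The effect is small if few decisions move (6.2% false positives with 10% withheld, against 5.1% with none) and material if many do (26.7% with 40%). Those figures assume a 25% true rate in both arms, a shift in one arm only and an uncorrected two-sided test; they are scenarios, not estimates. The point is conditional on repeat reduction being primary, so Ib, the Number of Subjects section and IIIb must first be reconciled. It calls for an inexpensive improvement before enrollment and does not show that the trial would be biased.

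**What to change.** Reconcile the primary outcome across Ib, Number of Subjects and IIIb. Then, leaving the clinical decision as it is:

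1. In Ic, state who decides on repeat reduction and, if that person is not blinded, say that this outcome is not blinded.
2. In Ic and IIIa, have the already planned blinded surgeon read angulation and displacement on the first post-casting film of every patient, taken before any repeat. Apply the protocol's age-based angulation limit at analysis, since the reader does not see age, once the sponsor has settled the unassigned age of exactly 10.
3. In Number of Subjects, prespecify a supporting analysis that cross-tabulates, by arm, the repeat decision against the blinded reading. Show displacement beside angulation so that repeats made for displacement are not counted as discordant, and interpret the repeat-reduction result alongside this table. This should be fixed in advance, because that section leaves further statistical development until after data are collected.

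The cost is protocol wording and a little extra analysis; the reader and the films are already planned. The downside is that a benefit on repeat reduction which the blinded reading does not support would have to be reported more cautiously.

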### **IIIb. Data Collection / Monitoring**

The primary endpoint of the study is comparing the percentage of patients with an adequate degree of angulation on post-reduction x-rays between the experimental group and the control group. X-rays will be performed based on the PED routine standard of care.

Demographic data recorded by the study trained physician will include the patient's name, age, medical record number, date of birth, date of visit, and ultrasound experience of the study-trained physician performing the ultrasound. *The patient identifiers are necessary for patient tracking to match ultrasound findings with X-ray final readings and for clinical follow up.* Type of sedation used, length of procedure and any ultrasound data will be collected and recorded by study trained physicians. Radiographic readings will be collected by the investigators.

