#### **IIId. Number of Subjects**

From a retrospective chart review sampling of displaced forearm fractures requiring reduction from June 1 to August 31, 2015 at CHAM, there were 20 displaced forearm fractures that underwent a closed reduction procedure in the Pediatric Emergency Department. 5 of the 20 displaced forearm fractures (25%) were inadequately reduced and required repeat reduction and/or operative management. Based on a recent study by Wellsh et al, only 6% of patients required repeat fracture reduction when US guidance was used.

In order to observe such a difference with 80% power, the sample size calculation would require a minimum of 56 patients in each group (standard of care vs US-guided reduction) with alpha set at P= 0.05.

Statistical significance will be assessed using mean, percentages, frequency distributions, and p-value. The significance will be set at 0.05. The test statistic used will be the Chi-square test. Confidence intervals will also be obtained. After the primary analysis of the group differences, logistic or normal regression will be used to determine factors related to these outcomes. The significance will be set at 0.05. The statistical approaches will be further developed with the assistance of the statistician in the orthopaedic surgery department following data collection and study approval.

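### The protocol names two different primary endpoints, repeat reduction and adequate angulation, and the sample size is not built cleanly on either

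*Combined protocol and SAP*

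**What the plan says.** Three places in the combined protocol and SAP define the endpoints.

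- **Section Ib, primary outcome:** "To compare the number of patients requiring a repeat reduction procedure between the experimental group" and the control group.
- **Section IIIb, Data Collection / Monitoring:** "The primary endpoint of the study is comparing the percentage of patients with an adequate degree of angulation on post-reduction x-rays".
- **Secondary Outcomes, item 2:** "To compare the adequacy of reduction between groups by measuring and comparing the degree of angulation and displacement on the post reduction x-rays". The item adds age-based limits for acceptable angulation and a reader blinded to group. Item 4 lists operative repair separately: "To compare the number of patients requiring operative repair after reduction between the experimental and control group".

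Section Ic confirms that "the orthopedic surgeon reading the x-rays and determining the degree of angulation and displacement will be blinded". Section IIIa leaves the decision to repeat a reduction to the orthopedic surgeon, as routine care, based on displacement on the post-reduction x-ray. It does not say that this surgeon is blinded.

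The Number of Subjects section does not name the endpoint it is sized for. Its control rate comes from a chart review: "5 of the 20 displaced forearm fractures (25%) were inadequately reduced and required repeat reduction and/or operative management". Its ultrasound rate comes from a cited study: "only 6% of patients required repeat fracture reduction when US guidance was used". From these, with 80% power and alpha 0.05, "the sample size calculation would require a minimum of 56 patients in each group".

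**The concern.** The two named primaries are related but are not the same variable. One is a treatment decision taken in routine care; the other is a measurement by a blinded reader against an angle limit. A patient can exceed the limit and not be re-reduced, or be re-reduced for displacement with angulation inside the limit. The two analyses can therefore disagree, and no rule says which one is the trial's result. The Number of Subjects section also defers further development of the statistical approach until after data collection, so the choice could be made with results in view.

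The sample size might have shown which endpoint was meant, but its two rates are worded on different definitions. The control rate includes operative management and the ultrasound rate does not mention it. Read literally, the Ib outcome gives a patient sent straight to surgery after a failed reduction no primary event, although the chart review counted such a patient as a failure. Secondary item 4 would still record the operation. A non-significant result would be hard to interpret when the only power statement is not established for either endpoint as worded.

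**Working it through.** **1. The endpoint statements side by side**

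| Place | Status given | Variable | Who determines it |
|---|---|---|---|
| Ib | Primary | Repeat reduction, yes/no | Surgeon in routine care (IIIa), not stated to be blinded |
| IIIb | Primary | Adequate angulation on x-ray, yes/no | Blinded reader (Secondary item 2, Ic) |
| Secondary item 2 | Secondary | Adequacy from angulation and displacement, with angulation limits | Blinded reader |
| Secondary item 4 | Secondary | Operative repair | Not stated |
| Number of Subjects, control 25% | Planning rate | Repeat reduction and/or operative management | Chart review, 5/20 |
| Number of Subjects, ultrasound 6% | Planning rate | Repeat reduction | Cited study |

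Ib and the secondary list agree with each other, so IIIb is the outlier. No section ranks them.

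**2. Reproducing the plan's figure**

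Inputs from Number of Subjects: p1 = 0.25, p2 = 0.06, alpha 0.05, power 80%, chi-square test. Assumed because not stated: two-sided, no continuity correction.

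n per group = [z(0.975)·√(2·p̄·(1−p̄)) + z(0.80)·√(p1(1−p1) + p2(1−p2))]² / (p1−p2)², where p̄ = (0.25 + 0.06)/2 = 0.155.

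- √(2 × 0.155 × 0.845) = 0.5118, and × 1.960 = 1.0031
- √(0.1875 + 0.0564) = 0.4939, and × 0.8416 = 0.4156
- (1.0031 + 0.4156)² / 0.19² = 2.0129 / 0.0361 = 55.8, rounded up to **56**

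This matches the plan. Power at 56 per group is 80.2%.

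**3. Power of 56 per group when both rates are on one definition**

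Power = Φ{[|p1−p2|·√56 − 1.960·√(2·p̄·(1−p̄))] / √(p1(1−p1) + p2(1−p2))}. The exact column enumerates the uncorrected chi-square test.

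| Definition and assumption | Control | Ultrasound | Power (formula) | Power (exact) | n for 80% |
|---|---|---|---|---|---|
| Repeat reduction; all 5 events included one | 25% | 6% | 80.2% | 83% | 56 |
| Repeat reduction; 1 event operative-only | 4/20 = 20% | 6% | 59.8% | 62% | 90 |
| Repeat reduction; 2 events operative-only | 3/20 = 15% | 6% | 34.1% | 34% | 181 |
| Composite in both arms; ultrasound 8% | 25% | 8% | 68.3% | 70% | 74 |
| Composite in both arms; ultrasound 10% | 25% | 10% | 55.2% | 57% | 100 |

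The first row is the plan's own pair. It applies equally to the composite if the 6% already includes operative cases. The other rows are assumptions: the split of the five events is not given, nor is it known whether the 6% includes operative cases. If it does not, the composite rate in the ultrasound arm cannot be below 6%. The last column is for scale only.

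Solving the power formula for 80% at 56 per group against 6% gives a control rate of 24.95% (24.2% by exact enumeration). Both lie above 4/20, so reclassifying one event is enough to lose 80%.

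**4. Scoring of direct-to-surgery patients**

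Expected control failures on the chart-review definition: 0.25 × 56 = 14. If one event in five is operative-only (assumption), the Ib outcome counts 0.20 × 56 = 11.2. The difference, 2.8 or about 3 patients, would be failed reductions scored as non-events on the primary.

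**5. The IIIb endpoint**

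No adequacy rate is given for either arm, so its power follows only from an assumption. If adequacy were exactly the complement of the planning rates (75% versus 94%), n is again 56. At 80% versus 94% power is 59.8%, and at 75% versus 90% it is 55.2%. No section states that equivalence.

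**6. Two primaries at 0.05 each**

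If either could be claimed, the false-positive rate is 5% with full overlap and 1 − 0.95² = 9.75% if the tests are independent. The overlap is not given.

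**The case against.** The strongest reply is that IIIb is a drafting slip. Ib and the secondary list are consistent, and the Number of Subjects section lies closer to Ib: the 6% is a repeat-reduction rate and the 25% includes repeat reductions. If all five chart-review patients had a repeat reduction, 56 per group is correctly powered for Ib, and no section says that any event was operative-only. On that view the lower power figures show sensitivity to an ambiguous label and not a demonstrated shortfall.

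Much of this is fair. The lower figures are illustrations, and one corrected sentence in IIIb would remove the contradiction. Secondary item 4 means that operated patients are not lost from the trial's data. Secondary item 2 is also not word for word the IIIb endpoint, since it covers displacement as well as angulation. The data list in IIIb names neither repeat reduction nor operative repair, but it may not be exhaustive, because IIIa mentions a data collection form that is not shown.

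The core is untouched. IIIb is an explicit statement of the primary endpoint in the current text, and an analyst could follow it in good faith. The different wording of the two planning rates is also on the page, whatever the five charts turn out to show.

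**Conclusion.** The concern holds and must be fixed before outcome data are seen. The plan as written allows two different primary results and gives no rule for choosing between them. This part needs no assumption.

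The sample size contains no arithmetic error. For the Ib outcome, 80% power is established only if all five of the 20 chart-review events included a repeat reduction. One operative-only event would bring it to about 60% and two to about 34%. For a composite in both arms, 80% stands if the ultrasound rate is 6%; at an assumed 8% or 10% it is about 68% or 55%. For the IIIb endpoint, power can be stated only under assumed adequacy rates. All power figures assume a two-sided test at 0.05 without continuity correction, 56 analysed patients per group and, unless marked exact, the pooled-variance formula.

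**What to change.** Name one primary endpoint and make Ib, the Secondary Outcomes list, Number of Subjects and IIIb agree. The smallest change has three parts:

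1. Keep the Ib outcome and reword the first sentence of IIIb so that blinded angulation adequacy is secondary, as in item 2.
2. State how a patient sent directly to surgery is scored. Either count repeat reduction and/or operative management as failure in both arms over one stated follow-up window, with operative repair still reported separately (this matches the 25% definition), or count repeat reduction only and use the repeat-only chart-review count as the control rate.
3. Report the split of the five chart-review events, check in the cited study whether the 6% includes operative cases, and restate the power of 56 per group with both rates on the chosen definition.

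If angulation adequacy is preferred as primary, obtain adequacy rates for both arms and redo the calculation.

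Two additions are useful but not needed to remove the contradiction: keep blinded angulation adequacy as a key secondary outcome, and state whether the surgeon deciding on re-treatment knows the arm. A re-treatment primary rests on a decision not stated to be blinded.

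The cost is wording in three sections, a second look at five charts, confirmation that repeat reduction and operative repair are captured on the data form, and tracing patients to the end of any stated window. The restated power may be less favourable. Raising the sample size is not required.
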